ClinicalTrials.gov Data Entry Cover Sheet

Today's date: May 15, 2024 **Document date:** November 15, 2023

Protocol ID: 21287 Clinical Trials.gov ID: NCT05129501

Project Title: The Impact of an Adapted Version of the Strengthening Families Program on IPV

Among Caregivers and ACEs Among Children

Principal Investigator: [name], University of Nebraska-Lincoln

Recruitment and Retention Plan

Careful efforts will be made to **maximize participant enrollment** and **minimize attrition** in the survey and programming portions of the project. As described in the Statistical Design and Power Analysis section of this proposal (referenced in C.14 of the Research Strategy), we will enroll a total of 320 families (160 per condition). Based on previous similar research, including the Pl's work, we anticipate that we will retain 75% of the sample at the 8-month follow-up for a final sample size of 120 families per condition (160 youth and 160 caregivers per condition x 2 conditions for a grand N = 640 youth and caregivers across conditions at the pretest, and 480 across conditions at the 8-month follow-up).

Recruitment

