Aim 2d. Structural equation modeling (MSEM) will be utilized via Mplus software to test whether the intermediary outcomes (child, caregiver, and family outcomes) at post-test are at least partial mediators of the effect of the program on the primary outcome of youth ACEs at follow-up and whether there are moderators of the effect of the program on youth ACEs. Evidence of mediation will be determined using the product of coefficients method using parametric bias-corrected bootstrapping with 1,000 resamples to calculate the confidence intervals (CI). To test for moderation for dichotomous variables (e.g., gender), we will estimate SEM multiple group models, first allowing estimation of the path coefficients to vary freely across groups, and then constraining paths to be equal when a structural path coefficient of interest was significant for one group and not the other group. We will conduct model comparisons using the chi-square ( $\chi^2$ ) difference test (i.e.,  $\chi^2$ , p < .05 indicating moderation). For continuous moderators, they will be operationalized as cross-product interactions with condition (all variables mean-centered). Significant interactions will be probed.  Models will be evaluated for overall model fit via  $\chi^2$  statistic, root mean square error of approximation (RMSEA  $\leq$  .08), the comparative fit index (CFI  $\leq$  .08), and the Tucker-Lewis Index (TFI  $\geq$  .90), as well as the significance and directionality of included path coefficients. Nesting will be accounted for, as needed.

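### Aim 2d asks what moderates the program's effect on youth ACEs, but it specifies only path-level tests in the SEM framework shared with mediation and no between-group test of the total effect

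*SAP*

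**What the plan says.** SAP, Outcome Analyses, Aim 2d, assigns two questions to SEM in Mplus. One is whether post-test intermediary outcomes are "at least partial mediators of the effect of the program on the primary outcome of youth ACEs at follow-up". The other is "whether there are moderators of the effect of the program on youth ACEs".

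- **Mediation:** "Evidence of mediation will be determined using the product of coefficients method", with bootstrap confidence intervals.
- **Dichotomous moderators such as gender:** "we will estimate SEM multiple group models, first allowing estimation of the path coefficients to vary freely across groups", followed by "constraining paths to be equal when a structural path coefficient of interest was significant for one group and not the other group". A chi-square difference test at the 5% level then decides whether there is moderation.
- **Continuous moderators:** "they will be operationalized as cross-product interactions with condition". The equation that holds the product term is not given.

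Aim 2c estimates the total effect of condition by ANCOVA, but describes no moderator term. On sample size, the protocol's Recruitment and Retention Plan states: "we anticipate that we will retain 75% of the sample at the 8-month follow-up for a final sample size of 120 families per condition".

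**The concern.** The program's effect on ACEs is the whole effect of being assigned to it, by whatever route. In a model with post-test mediators, this effect is split into a direct path and indirect effects through the mediators. No step in Aim 2d puts the parts together again and compares the sum between groups.

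Two errors can follow if the mediators are in the moderation model:

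- **Missed moderation.** The program may help one gender more because it shifts the mediators more in that gender. The direct paths can then be equal although the benefit differs.
- **Moderation reported where there is none.** Total benefit may be equal while the route differs. Single paths then differ, and the stated rule labels this moderation.

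The direct path is also estimated conditional on a variable measured after randomization, so it no longer has the protection of randomization. ACEs are the primary outcome, and a statement about who benefits may influence who is offered the program.

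**Working it through.** **Sample size.** 160 × 0.75 = 120 families per condition, as the protocol states. With an assumed 50/50 split on the moderator, this gives 60 per group-by-condition cell. The text reviewed gives no power or effect size for moderation, so there is no moderation figure to reproduce.

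**Model.** In each group, *a* is the path from condition to mediator, *b* from mediator to ACEs, and *c′* from condition to ACEs given the mediator. Total effect = *c′* + *a·b*.

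**Assumptions (none from the documents).** One mediator with unit residual variance; *b* = 0.5 in both groups; within-arm SD of ACEs equal to 1, so the residual variance of ACEs given the mediator is 1 − 0.5² = 0.75; no covariates or clustering.

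**Standard errors of the between-group differences, 60 per cell.**

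- Total effect, and likewise path *a*: √(4/60) = 0.258.
- Direct path: √[0.75 × (2/60) × (v₁ + v₂)], where v = 1 + a²/4 in each group.

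**Case A: equal totals, different routes.** *a* = 0.7 and 0.1; *c′* = 0.05 and 0.35. Totals: 0.05 + 0.35 = 0.40 and 0.35 + 0.05 = 0.40.

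- Direct path: v = 1.1225 and 1.0025, SE = √(0.025 × 2.125) = 0.230. 0.30/0.230 = 1.30, so it rejects in about Φ(1.30 − 1.96) ≈ 26%.
- Path *a*: 0.6/0.258 = 2.32, so it rejects in about Φ(2.32 − 1.96) ≈ 64%.
- Total effect: true difference 0, so 5%.

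**Case B: total 0.5 versus 0, half mediated.** *a* = 0.5 and 0; *c′* = 0.25 and 0.

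- Total effect: 0.5/0.258 = 1.94, power about 49%.
- Direct path: SE = √(0.025 × 2.0625) = 0.227. 0.25/0.227 = 1.10, power about 20%.

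**Case C: total 0.5 versus 0, fully mediated.** *a* = 1.0 and 0; *c′* = 0 in both. The total effect again has about 49% power. The direct path has a true difference of 0, so 5%.

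Simulation agrees. It also gives the chance that at least one of the three paths is flagged under the plan's rule, meaning that it is significant in only one group and differs significantly between groups:

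| Case | Direct path | Any path, plan's rule | Total effect |
|---|---|---|---|
| A: equal totals | 26% | 72% | 5% |
| B: 0.5 vs 0, half mediated | 18–20% | 54% | 49% |
| C: 0.5 vs 0, fully mediated | 5% | 93% | 49% |

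The first and last columns apply no pre-filter. With no moderation of any kind (*a* = 0.5, *b* = 0.4, *c′* = 0 in both groups), some path is flagged in 7.5%. With all 320 families (80 per cell), the direct path in Case A rejects in 32%.

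**Other path sizes.** With *a* = 0.8 versus 0, *b* = 0.5 and *c′* = 0 versus 0.4 (total 0.40 in both), the direct path rejects in 40%, some path is flagged in 89%, and the total effect rejects in 5%.

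**The pre-filter alone.** With *a* = 0.5, *b* = 0.4, and *c′* = 1.3 versus 0.6, both groups are usually significant on the direct path. The unfiltered direct-path test rejects in 81.5% and the filtered one in 6.4%. The total-effect test rejects in 77.6%. This loss comes from the filter and not from the direct/total distinction.

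**The case against.** **The mediators may not be in the moderation model.** A reader might infer from Aim 2d that moderation is definitely tested inside the mediation SEM. The text does not say so. It gives mediation and moderation separate methods, and a product of moderator and condition is an ordinary total-effect test. Several path coefficients would also arise from covariates, and the fit indices could refer to the mediation models or to a latent outcome. If the model holds only condition, covariates and ACEs, the condition path is the total effect and the direct-versus-total problem falls away. This stands. The mediation reading is still the more natural one, because the only structural model Aim 2d describes has the mediators between condition and ACEs, and fit indices say nothing about a saturated one-path model.

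**Moderation through the mediators need not be missed.** A reader might also conclude that a difference in benefit carried by the mediators would go undetected. That follows only if the direct path alone is compared. The plan refers to paths without naming them. If all are compared, Cases B and C are flagged in 54% and 93% of trials. This largely removes the missed-moderation error, but it makes the opposite one worse: 72% flagged in Case A. Path *a* truly differs there, so the path test is right about the path; it is the answer to the stated question that is wrong.

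**The sizes are assumed.** The documents give no path sizes, and Case A needs direct and indirect effects that offset each other. The percentages are illustrations. The direction follows from total = direct + indirect.

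**Unseen text and scope.** Part of the SAP and the logic model in the Research Strategy were not available for this review and may define the path of interest. The Aim 2c main effect is not affected.

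**Conclusion.** The point holds in a conditional form. Aim 2d poses a total-effect question and, in the text available, describes no between-group test of the total effect. It also leaves open whether mediators are in the moderation model and which path decides. With mediators included, single-path tests answer a different question: in Case A about 26% (direct path) or 72% (any path under the plan's rule) of trials would report moderation of an effect that is equal in both groups, against 5% for the total-effect test. A direct-path test alone has 5% to 20% power in Cases B and C, where the total-effect test has 49%. These figures rest on one mediator, an even split of the moderator, 60 per cell and the assumed path sizes. The documents do not support saying that the plan certainly tests only the direct effect, or that it will miss moderation. The plan should be changed, because the open choice decides what a moderation finding on the primary outcome means.

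**What to change.** For each moderator, state in Aim 2d that moderation of the program's effect is judged by the condition-by-moderator term in a model for follow-up ACEs with the pre-test covariates and no post-test mediators. In multiple-group form, this is an equality constraint on the condition-to-ACEs path of that model. If the mediation SEM is kept for this purpose, define direct plus indirect effect as one parameter and test its between-group difference. Choose one of the two in advance.

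Run the test whatever the within-group significance. Report between-group differences in individual paths separately, as secondary moderated mediation. Because power is only about 49% for a 0.5 SD difference between groups under the assumptions above, report the interaction with its confidence interval and do not read a non-significant result as equal benefit.

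Cost: SAP wording and one simple model per moderator, with no new data.

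### For dichotomous moderators, the test for moderation runs only when a path is significant in exactly one subgroup, so other differences go untested and power can be lost

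*SAP*

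**What the plan says.** Aim 2d of the SAP (Outcome Analyses) asks, among other things, "whether there are moderators of the effect of the program on youth ACEs", with youth ACEs as the primary outcome. Two procedures are given, depending on the type of moderator.

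- **Dichotomous:** a multiple-group SEM is fitted first, with each subgroup keeping its own path estimates. The equality step comes second and is conditional: "and then constraining paths to be equal when a structural path coefficient of interest was significant for one group and not the other group". Free and constrained fits are then set against each other by a chi-square difference test, and the decision rule is "p < .05 indicating moderation".
- **Continuous:** here the SAP sets no condition on within-group results and models the interaction at once: "they will be operationalized as cross-product interactions with condition (all variables mean-centered").

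The SAP text reviewed describes no test for a path that is significant in both groups or in neither.

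**The concern.** Moderation is a statement about the difference between two subgroup effects. Whether each effect falls on one side or the other of p = 0.05 does not measure that difference. Used as the condition for running the test, it leaves three situations without one:

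- both effects significant in the same direction but of different size;
- both significant in opposite directions;
- neither significant, although they differ from each other.

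The second would be benefit in one group and harm in the other, which is the form of moderation one would least want to leave without a formal result. The same scientific question also gets two decision rules, depending only on whether the moderator is dichotomous or continuous.

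Two limits should be clear. The SAP does not declare moderation merely because one subgroup is significant and the other is not; the formal test is still required. The issue is therefore lost power, not extra false claims, and it does not reach the main comparisons of Aim 2c.

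**Working it through.** **Inputs from the documents.** The Protocol (Recruitment and Retention Plan) enrols 160 families per condition and expects 75% retention, "for a final sample size of 120 families per condition". This reproduces: 160 × 0.75 = 120. The difference test is at 0.05, with 1 degree of freedom per constrained path.

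**Assumptions, not in the documents.** The moderator splits 50/50, giving 60 families per condition in each subgroup. Residual variance is 0.75 on a standardised outcome (25% explained by covariates). The path estimates are normal, there is no clustering, and within-group significance is two-sided 0.05. The effect sizes are illustrative.

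**Formulas.**

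- Standard error of each subgroup effect: √(2 × 0.75/60) = 0.158.
- Standard error of the difference: √(0.158² + 0.158²) = 0.224.
- Always-test rule: declare moderation if (b₁ − b₂)²/(SE₁² + SE₂²) > 3.841.
- Stated rule: the same test, but only if exactly one of |b₁/SE₁| and |b₂/SE₂| exceeds 1.96.

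The stated rule rejects on a subset of the occasions on which the always-test rule rejects, so its power can never be higher.

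**Worked case, +0.4 and −0.4 SD.** Each subgroup has expected z = 0.4/0.158 = 2.53 and is significant in its own direction with probability 0.716. Both are significant in 0.716² = 51% of trials, and no test is run. Exactly one is significant in 2 × 0.716 × 0.284 = 41%. The difference has expected z = 0.8/0.224 = 3.58, so the always-test power is Φ(3.58 − 1.96) = 95%. Integrating over the gate leaves 39%.

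**Power by scenario** (numerical integration; effects in SD):

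| Effects in the two subgroups | Always test | Stated rule | Test is run in |
|---|---|---|---|
| 0.5 / 0 | 60.9% | 57.6% | 84.7% |
| 0.4 / 0 | 43.2% | 39.3% | 69.4% |
| 0.5 / 0.2 | 26.9% | 26.2% | 69.7% |
| 0.4 / −0.1 | 60.9% | 49.9% | 67.4% |
| 0.9 / 0.4 | 60.9% | 26.3% | 28.4% |
| 1.0 / 0.5 | 60.9% | 11.2% | 11.5% |
| +0.3 / −0.3 | 76.5% | 45.1% | 49.9% |
| +0.4 / −0.4 | 94.7% | 39.4% | 40.7% |
| +0.5 / −0.5 | 99.4% | 20.1% | 20.3% |

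In the last three rows the chance of detection falls as the true difference grows, because both paths become significant and the test is skipped.

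**Neither path significant.** With equal standard errors, z for the difference can still approach 2 × 1.96/√2 = 2.77, above 1.96. Differences that would be significant are therefore missed here too: 8.9 points of power at +0.3/−0.3.

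**Sensitivity.** With residual variance 1.0: 64.2% against 40.4% at +0.3/−0.3, and 87.3% against 45.5% at +0.4/−0.4. With a 60/40 split and variance 0.75: 74.8% against 44.7%, and 93.9% against 41.0%.

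**False positives.** With no moderation, the stated rule declares it in 3.1% (no effect in either group), 4.9% (0.3 in both) and 4.6% (0.4 in both). The largest value over equal effects from 0 to 1.0 SD is 4.9%. Among paths that reach the test, however, 33%, 10% and 11% respectively are called moderated. The p-value of a path selected this way is therefore not a 5% test given the selection.

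**The case against.** The case on the other side is about weight, and parts of it stand.

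- **The opposite-sign losses are partly a missing formality.** If both paths are significant with opposite signs, the difference has |z| of at least 2.77 with equal standard errors, so the skipped test was certain to reject. A reader of the free model would see both coefficients. This accounts for about 51 of the 55 points lost at +0.4/−0.4, and about 23 of the 31 lost at +0.3/−0.3. This stands as a qualification. The plan still gives no rule by which moderation would be declared there, and a test added after seeing the subgroup results would be unplanned. The argument also does not cover same-direction differences such as 1.0/0.5, where the coefficients alone do not settle the matter.
- **For moderate effects in the same direction the loss is about 1 to 3 points** (0.3/0.1: 14.5% against 13.3%; 0.6/0.3: 26.9% against 23.7%), and the direct test is itself weak. This stands. A mild reversal costs more (0.4/−0.1: 11 points).
- **The effect sizes are assumed.** This also stands. The Protocol refers to a power section that is not among the text reviewed, so the absence of an effect size is not counted against the plan.
- **Testing every path has a multiplicity cost.** With no true effects the gate opens for 9.5% of paths, whereas the fix tests all of them. For an assumed 10 independent null paths, the chance of at least one false claim rises from 1 − 0.969¹⁰ = 27% to 1 − 0.95¹⁰ = 40%. That is a reason to limit and prespecify the paths. It does not justify a gate that does not measure the difference.

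**Conclusion.** The concern holds. As written, the rule for dichotomous moderators leaves some subgroup differences without a formal test and never has more power than testing directly. How much is lost depends on the true effects. It is roughly 1 to 4 points when one subgroup alone responds or both respond modestly in the same direction. It is about 30 to 80 points when effects of 0.3 to 0.5 SD run in opposite directions, or when both effects are large and unequal. These figures rest on 120 families per condition, the assumed split and variance, and an approximately normal outcome without clustering; the pattern persists under the alternatives tried. Per-path type I error is not inflated and Aim 2c is untouched. The change should be made, because it concerns a stated aim on the primary outcome and is easy to make, but the main trial result does not depend on it.

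**What to change.** Replace the conditional step in Aim 2d with one sentence: for every prespecified path and dichotomous moderator, the free and equality-constrained models are compared by the chi-square difference test (or the condition-by-moderator interaction is tested), regardless of within-group significance. Report the subgroup difference with its confidence interval, and treat within-group p-values as descriptive. This also brings dichotomous moderators into line with continuous ones.

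No new data are needed. The cost is more tests to report and a per-path false-positive rate that rises from 3.1–4.9% to the nominal 5%. Because the family-wise rate rises with the number of tests, the paths and moderators should be listed in advance and their number stated with the results.
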